University of Pennsylvania School of Medicine Hospital of the University of Pennsylvania

[name], Clinical Research Coordinator Department of Radiology

Community Support Program for Lung Cancer Screening

NCT06207435

UPCC 07523

Study Protocol and Statistical Analysis Plan

04/13/2023

[name]

Clinical Research Coordinator
Department of Radiology | Interventional Radiology
[name]
[name]
[name]
[contact]

Community Support Program for Lung Cancer Screening

Abstract

Lung cancer screening (LCS) using low-dose CT (LDCT) for high-risk individuals is a critical public health tool for reducing lung cancer mortality. Despite the recent expansion of the inclusion criteria to be more equitable, uptake and adherence remains low and is lowest among low-income and racial/ethnic minority populations and in individuals with a negative baseline screening study (Lung-RADS 1&2). Community-based programs promoting cancer screening uptake have demonstrated increased screening engagement compared to clinic-based programs in reaching disadvantaged individuals but suffer from lack of robust funding and limited data demonstrating impact on a population level. Community-based participatory research (CBPR) utilizes a partnership approach, bringing together researchers and community stakeholders as equal partners throughout the research process to contribute expertise and share in decision making. CBPR has demonstrated the ability to reduce cancer health disparities and reduce mistrust between academia and surrounding communities through reciprocal learning.

The overall objective of this project is to demonstrate the impact of a community support program (CSP) on improve adherence to LCS follow-up guidelines in an urban environment. This project aims to collaborate with community partners to develop an infrastructure and iterative process to provide social support to community members that facilitates obtaining their follow-up LDCT for LCS. It utilizes novel population level data that includes geospatial analysis of neighborhood-level data of patients residing in Philadelphia who have received a LDCT for LCS. This allows for targeted community level interventions and the ability to evaluate impact on a population level.

We will target individuals in our healthcare system residing in Philadelphia with a negative baseline screening CT and an upcoming or missed follow-up screening CT. Participants will be divided into receiving clinic + community support vs routine clinic only (control) based on residential location. The intervention group, consisting of individuals residing in West Philadelphia, will receive the option of enrolling in the CSP for obtaining their recommended LDCT. Community members designated as CSP representatives will receive basic training about LCS, transportation vouchers and information regarding other support services. They will also provide feedback to inform an interactive approach to reevaluating the intervention throughout the course of the study. Primary analysis will measure the 12-month follow-up LDCT adherence rate difference between clinic + CSP group vs clinic only group and its association with CSP enrollment. Additional analyses will measure differences in follow-up LDCT utilization before vs after intervention and extent of enrollment in the CSP in the intervention group. Planning and evaluation of our program will be performed using the widely utilized RE-AIM framework with emphasis on measuring reach, effectiveness, and sustainability of our approach.

Hypothesis: A community support program to facilitate lung cancer screening appointments will improve adherence to yearly follow-up screening compared to routine care alone.

Detailed Research Plan

Significance and Rationale:

Lung cancer remains the leading cause of cancer deaths in the United States, accounting for 25% of all cancer deaths¹. Despite the established impact of lung cancer screening (LCS) with low-dose CT (LDCT) and coverage by major health insurances, less than 5% of all eligible individuals receive recommended screening^{2,3}. Furthermore, there are significant disparities in the uptake of recommended LCS in the US on the basis of sociodemographic factors, with individuals who are black, low-income, underinsured, with low education levels, and residing in underserved urban or rural communities having lower rates of LDCT screening uptake⁴⁻⁷. For example, eligible black patients were 2.8 times less likely to receive LDCT⁴ and were also less likely to complete follow-up after an initial baseline screening⁸. This is not inconsequential given the pre-existing disparities in incidence, stage of detection and mortality from lung cancer. For example, black patients are more likely to present at a younger age, at more advanced stages⁹, and have reduced survival compared to white patients^{9,10}. Furthermore, current cigarette smoking—one of the strongest risk factors—is highest among vulnerable patient populations and lower socioeconomic status^{11,12}. These trends in screening uptake risk even further exacerbation of disparities in lung cancer outcomes over time.

This study aims to address disparities in lung cancer screening (LCS) adherence using principles of community based participatory research (CBPR) to implement a community support program (CSP) for LCS. By bringing researchers and community stakeholders together as equal partners in decision-making and knowledge sharing, CBPR has demonstrated an ability to reduce health disparities and reduce mistrust between academic and surrounding communities^{13–15}. It has also been shown to improve health literacy in underserved populations^{16,17} which is an independent predictor of adherence to screening programs across multiple cancer types¹⁸. Interventions applying principles of CBPR have taken the form of decision aids^{19,20}, patient navigators and 'citizen scientist'^{21–25}, and mobile clinics²⁶ and have shown positive impact in cancer screening uptake and patient satisfaction among underserved populations, including in LCS. Although there is extensive evidence of the efficacy of community-based cancer prevention programs in improving knowledge and screening uptake, demonstration of their impact in reducing health disparities on a population level remains a challenge²⁷. *Our study design overcomes this challenge by utilizing novel population-level data that includes geospatial analysis of neighborhood-level data of patients residing in Philadelphia who have received a LDCT for LCS, allowing for a targeted population-level intervention and robust impact evaluation.*

The proposed intervention will be guided by the RE-AIM (Reach Effectiveness Adoption Implementation Maintenance) framework, a robust implementation strategy, widely applied to interventions at the community and population-health levels. With the principal concepts of pragmatic engagement of various stakeholders and iterative reevaluation across multiple domains throughout all stages of an intervention, RE-AIM provides a framework for planning and measuring impact of health promotion and disease prevention initiatives with focus on sustainability^{28–30}. Utilization of a robust planning and evaluation framework is critical to ensuring external validity and sustainability of community-based interventions. *Our study aims to leverage an existing strong community partnership, novel population-level data, and robust research and evaluation frameworks to implement a scalable intervention to reduce disparities in LCS adherence.*

[figure not shown]
Specific Aims and Objectives:

- 1. Develop a community support program for lung cancer screening adherence
- 2. Measure the impact of the community support program in improving adherence to lung cancer screening follow-up

Innovation: This study leverages novel neighborhood-level data to design and evaluate a community-based intervention using a robust implementation science framework, RE-AIM. This design allows for measuring impact on a population level thereby overcoming a common limitation of community-based interventions²⁷. Our utilization of CBPR builds on a strong collaborative community partnership with an extensive track record of successful community-based events. Led by members of the study team, our department has collaborated with the Community of Compassion CDC community center in West Philadelphia over the past two academic years to offer 3 events to the surrounding community (see letter of committment). This would support a seamless

incorporation of CBPR, an approach that is strikingly absent from the radiology literature despite evidence of its effectiveness in reducing disparities in cancer health outcomes.

Preliminary Data: Using data from our NCI-funded Population-based Research to Optimize the Screening Process (PROSPR) Center, which assesses LCS outcomes in five diverse healthcare systems³¹, we observed low adherence rates to LCS recommendations (55% across five systems; 36% overall at Penn Medicine)³². Adherence is significantly lower in Black patients at Penn Medicine and varies by baseline Lung-RADS score (21%-70% in Black patients; 32%-88% in White patients). Additionally, adherence is lower among patients living in impoverished neighborhoods (44% vs 63% in highincome neighborhoods). Geospatial analysis for neighborhood-level data of the 349 and 1,328 Philadelphia residents who received LCS in 2020 and 2021 respectively was applied to support our

intervention at the planning district level (Figure 1). West and Southwest districts contained 28% and 19% of all patients respectively. For residents who received a LDCT in 2020 with a Lung-RADS 1 or 2 recommendation,

which accounted for 90% of all studies, adherence to a 12-month follow-up study in 2021 was 24%. Data collection from 2022 is still in progress so estimates from 2020 and 2021 were utilized.

A questionnaire developed by [name] in 2017 was administered to patients visiting Temple University Hospital Radiology Department as part of an effort to understand modifiable patient barriers to LCS in North Philadelphia³³. It was completed by 124 predominantly African American patients with health insurance. The average score was 33% on items accessing knowledge about LCS. Perceived cost and inability to get out of work were the top two reported reasons for lack of adherence to appointments. These preliminary data, supported by review of the literature, informed our initial approach to reducing barriers to LCS adherence.

The Philadelphia Lung Cancer Learning Community (PLC2) is a collaborative agreement involving a multidisciplinary team across Jefferson Health, Penn Medicine, and Temple Health that aims to decrease lung cancer morbidity and mortality across the greater

[figure not shown]

Fig 2. Philadelphia Neighborhood Characteristics. Neighborhood-level data were mapped for each Planning District or Census Tract in the city of Philadelphia.

Philadelphia region by developing and implementing effective ways to increase LCS and tobacco treatment, particularly in populations at greatest risk. The PLC2 has systematically characterized LCS using a city-wide, multi-institutional approach and applied geospatial analyses for neighborhood-level data³⁴ (Figure 2). This allows for comprehensive strategies that integrate population health approaches and the ability to measure impact on a population health level. Our data sharing and collaboration agreement would support scaling our intervention to a multi-institutional and city-wide level for external validation and increased population impact. Experimental Design and Methods:

Specific Aim 1. Develop a community support program for lung cancer screening adherence A consortium of representatives chosen by an established community center with a track record of providing social services to their surrounding communities and Penn Fig 3. Monthly Medicine multidisciplinary team will be formed and will work to develop rules of 1 week "Sprints" operation and decision making for the community support program (CSP). Penn Medicine team members include researchers in radiology, implementation science and CBPR and a patient navigator (PN). CSP representatives will be individuals chosen by our partner community center that have demonstrated commitment and prior experience in providing social support to their surrounding communities. The consortium members will meet over the course of 2 weeks at the commencement of the Sprint study to agree on goals, timeline, organizational structure, and 4 Weeks standardized processes. Using the collaborative principles of CBPR, representatives from academia and the community will engage in reciprocal learning sessions to create CSP material that is socially and culturally sensitive to the needs of the community. Initial community support will be developed based on preliminary data and evidence that two of the main barriers to utilization of lung cancer **Planning**

about lung cancer screening^{35,36}. We therefore propose providing transportation assistance and education augmentation. In addition, resources will be allocated to provide additional support throughout the study period based on feedback from CSP representatives.

screening are transportation cost/availability and limited education

Education: CSP representatives will be trained about the basics of lung cancer screening needed to provide support for patients with an upcoming LDCT appointment. Patient-facing LCS material, adapted from ACR and Penn Medicine websites³⁷, will be created to ensure a fifth-grade readability level and sensitivity to local context in collaboration with a PN experienced in patient education and the CSP representatives. To adapt resources for fifth-grade readability, we will utilize an interactive process guided by resources from LUNGevity³⁸ and the Centers for Medicare and Medicaid Services (CMS) health literacy resource toolkit for making written material clear and effective⁴². Readability will be assessed with a commercial web-based suite of tools (readable.com) using a mean score from multiple validated indices ^{39,40,41}. Patient LCS education material would include information on lung cancer, cost and payment options, risks and benefits of screening, radiation exposure, treatment options and smoking cessation.

Transportation: We will utilize the Uber or Lyft transportation vouchers to provide rides to participants from their home location in West Philadelphia to and from the Penn Medicine downtown hospital locations on the day of their LCS study. Transportation vouchers will be created at an upper limit of \$30, which is expected to result in no out of pocket cost for most patients. The mean distance from the patient's residential address to the closest Penn Medicine hospital location is 2 miles and an approximate round trip ride costs \$22. Participants will also be given the option of a CSP representative arranging their transportation if they do not have access to Uber or Lyft transportation software. Based on projections from our preliminary data, allocation would be made to provide transportation support to 450 patients throughout the study period.

The CSP program will be set up to have month-long intervention periods that end with a review process and planning for the next intervention period, utilizing the agile principle of sprint planning⁴³ (Figure 3). This process

will allow for iterative changes that incorporate feedback from CSP representatives and foster an equitable research partnership. The radiology PN and CSP representatives will meet weekly to discuss day-to-day activities and hurdles and maintain an open line of communication for daily interactions. Time-sensitive issues will trigger consortium meetings separate from the scheduled monthly review meetings. The initial and monthly consortium meetings will be guided by the RE-AIM framework with emphasis on improving the reach, effectiveness, and maintenance of our interventions (Table 1). The meeting following the 6-month intervention period will be focused on future planning. The Mixed Methods Research Lab (MMRL), under the guidance of co-investigator [name], will provide technical support to facilitate and evaluate the equitable inclusion of the various stakeholder perspectives into the study design and interactive changes.

Table 1. Demonstrating the RE-AIM planning and evaluation metrics

RE-AIM components	Question answered	Metric	Future Planning
Reach	How many patients that were offered entry into the community support program engaged with the representative Reasons for non-participation in program.	Number of patients who chose community support / total number of patients who were offered it; demographic and geographic differences of patients reached vs. not reached	Identify potential reasons for patients not choosing community support Identify other possible forms of community support.
Effectiveness	Did addition of community support option lead to increased adherence to follow-up recommendation?	% Of patients who obtained yearly follow- up LDCT in intervention vs control groups % Of patients in intervention group who obtained yearly follow-up LDCT after intervention vs during a similar prior time frame	Identify and compare characteristics of adherent vs non-adherent patients Capture any unintended consequences of community support for LCS Capture additional barriers to LCS adherence
Maintenance (Sustainability)	If the lung cancer screening community support program is effective, how can it be sustained?	Measure actual cost of community support program	Explore options for additional funding including through grants and institutional support Explore institutional return on investment for increased lung cancer screening utilization through community support program

Specific Aim 2. Measure the impact of the community support program in improving adherence to lung cancer screening follow-up.

A prospective study would be designed to measure the impact of the CSP on a population level by utilizing aggregated neighborhood level data. The database contains information of patients who received baseline LCS with individual level residential address geocoded to determine neighborhood level characteristics (see preliminary data). The West Philadelphia planning district will be chosen as the intervention group because it is within the catchment area of Penn Medicine, has the highest number of LCS patients and is one of the districts noted to have consistent high rates of smoking prevalence and lung cancer mortality. In addition, we have strong community partnerships in the region. The control group would be individuals residing in the adjacent Southwest Philadelphia planning district which has a similar Yost score - a composite index of socioeconomic status⁴¹. Patients will be stratified into those with upcoming or missed appointments with primary analysis focused on patients with upcoming appointments. Informed consent will be provided prior to patient inclusion in the CSP. All activities will be approved by our Institutional Review Board prior to study commencement

We will identify patients residing in West Philadelphia who underwent lung cancer screening in 2020-2022 with a Lung-RADS 1 or 2 result and have an upcoming or missed appointment in our healthcare system downtown hospitals. We will analyze the EHR and RIS data to identify dates of LDCT upcoming appointments over 6 consecutive months with plans for 6 monthly cycles of intervention (Figure 3). A trained radiology PN will contact patients two weeks prior to their upcoming appointment, provide descriptions of the CSP and offer participation. Patients who agree to participate in the CSP would be contacted by a community representative

1 week and 1 day prior to their appointment to offer support based on their identified needs and the available resources. The CSP representatives will be provided transportation vouchers, educational material and resources for other social support and liaise with the radiology PN to report information from patient encounters including additional needs and patient plans to attend appointments. Patients with missed follow-up appointments who still receive care at Penn Medicine will be contacted by the radiology PN for inclusion in the CSP program. The CSP representative will offer appointment support and collaborate with the radiology PN to offer a rescheduled LDCT appointment to this group of study participants.

Recruitment and Sample: The eligibility criteria for study inclusion are 1) obtained LDCT in 2020-2022 with a Lung-RADS 1 or 2 result 2) upcoming or missed follow-up LDCT 3) residence in the city of Philadelphia. Preliminary data revealed that 1,328 individuals residing in Philadelphia received a LDCT in 2021, 90% of which are Lung-RADS 1 or 2. Assuming the same number of patients receive LCS in 2022 and follow-up LDCT scans are evenly distributed throughout the year, we anticipate that 598 individuals will have an **upcoming LDCT study** in the first 6 months of 2023 of which 167 (28%) in West and 114(19%) in Southwest planning district will be included in our primary analysis. For secondary analysis, patients residing in West Philadelphia (28%) with **missed appointments** (66%) following a Lung-RADS 1 or 2 recommendation on LDCT(90%) in 2020 and 2021 will be included, resulting in an additional 278 patients.

Evaluation: Evaluation will be guided by the RE-AIM framework with focus on Reach, Effectiveness and Maintenance of our program (Table 1). Primary outcomes of the study include: 1) difference in obtaining the recommended follow-up LDCT screening study in patients with upcoming appointments between the intervention and control group 2) association between participation in the CSP and adherence to follow-up LDCT. An intention-to-treat approach will be used for our primary analysis to measure the effectiveness of the CSP and will be done 2 weeks after completion of the 6-month intervention period. Chi-squared test will be used to measure a difference in adherence to follow-up LDCT between groups. A logistic regression model will be used to determine the association between adherence and utilization of CSP while controlling for demographic, geographic and socioeconomic variables. Secondary outcomes include: 1) difference in follow-up LDCT utilization in the intervention group compared to a similar period prior to implementation of CSP 2) reach of the CSP (what percentage of participants who were offered it engaged with the CSP representative). Evaluation of reach of the CSP would include descriptive analysis to evaluate differences in characteristics

the CSP and those who did not. Secondary analysis will include patients with **upcoming and previously** missed appointments following a negative screening study from 2020-2022. Mcnemar's test will be used to measure a difference in follow-up LDCT utilization after the

intervention compared to a similar

between participants who utilized

Table 2. Deliverables and Timeline (assuming start date of 11/1/2022)			
Deliverable	Target		
	Completion		
IRB Approval	11/30/2022		
Identification of CSP Representatives	11/15/2022		
Establishment of Consortium	11/30/2022		
Development of Support Material: Education, Transportation etc	12/31/2022		
Initiation of the CSP	01/01/2023		
Completion of the CSP	06/30/2023		
Data and Feedback Analysis	07/31/2023		
Manuscript and Presentation Preparation	09/30/2023		
Develop Structure for Future City-wide CSP	10/31/2023		

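### The stated target is patients with a negative baseline scan, but eligibility and the planning count accept any Lung-RADS 1 or 2 scan from 2020-2022, so repeat screeners are included and no index scan is fixed.

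*Combined protocol and SAP*

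**What the plan says.** The Abstract describes the target population in terms of the first screen: "We will target individuals in our healthcare system residing in Philadelphia with a negative baseline screening CT".

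The operative text is broader. Recruitment and Sample states: "The eligibility criteria for study inclusion are 1) obtained LDCT in 2020-2022 with a Lung-RADS 1 or 2 result". The second criterion adds an upcoming or missed follow-up, and the third adds residence in Philadelphia. Specific Aim 2 finds West Philadelphia patients by the same rule, as those who "underwent lung cancer screening in 2020-2022 with a Lung-RADS 1 or 2 result and have an upcoming or missed appointment". Neither place asks that the qualifying scan be the first or the most recent, and there is no exclusion for earlier rounds or for a later positive scan.

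The planning count starts from everyone in the city who had an LDCT in 2021, takes 90% as Lung-RADS 1 or 2, halves that for six months, and applies the district shares to reach 167 (West) and 114 (Southwest).

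Two passages lean towards a narrower reading. Specific Aim 2 says: "The database contains information of patients who received baseline LCS". Recruitment and Sample describes missed appointments as "following a Lung-RADS 1 or 2 recommendation on LDCT(90%) in 2020 and 2021".

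Under Evaluation, the first primary outcome is compared between districts with an unadjusted chi-squared test. The second relates adherence to programme use in a logistic model adjusted for demographic, geographic and socioeconomic variables. Screening history is not among them.

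**The concern.** With annual screening and a three-year window, one patient can have two or three scans. If no index scan is named, three things are left open.

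- **Population.** Someone scanned in 2021 who came back in 2022 and is due again in 2023 meets the criteria, yet is not a patient awaiting follow-up of a baseline scan. A result reported for the Abstract's population would rest on a broader one.
- **Classification.** Someone scanned in 2020 who missed 2021 and returned in 2022 could be counted as missed or as upcoming, depending on which scan is used. The plan stratifies on that split and restricts the primary analysis to upcoming appointments.
- **Confounding.** Allocation is by residence, not by randomisation, and programme use is the patient's choice. A patient who has already returned once may be more likely both to accept support and to attend. If so, the association between programme use and adherence is confounded by screening history. The district comparison is affected only if West and Southwest differ in their mix of first and repeat screens.

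**Working it through.** **Inputs.** From Preliminary Data: 349 and 1,328 Philadelphia residents screened in 2020 and 2021; 90% Lung-RADS 1 or 2; 24% adherence in 2021 after such a scan in 2020; district shares 28% and 19%. From Recruitment and Sample: 2022 volume equal to 2021, spread evenly over the year. From Power Considerations: N = 281, W = 0.17, 80% power, two-sided 5%.

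**1. The plan's own figures.**
- 1,328 × 0.90 × 0.5 = 597.6, stated as 598.
- 598 × 0.28 = 167.4 and 598 × 0.19 = 113.6, stated as 167 and 114.
- Noncentrality N × W² = 281 × 0.17² = 8.12. On 1 df this gives power 0.813, in line with the stated 80%. The W detectable with exactly 80% power is 0.167.

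The figures reproduce. They describe all recipients of an LDCT, not first scans.

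**2. Repeat share from the two stated yearly volumes.** Returners in 2021 = 349 × 0.90 × 0.24 = 75. As a share of 2021 scans, 75 / 1,328 = 5.7%. Carried over to the primary set, 281 × 0.057 = 16.

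**3. Repeat share in 2022 if 24% also applied to 2021 scans (assumption).** 1,328 × 0.90 × 0.24 = 287, and 287 / 1,328 = 21.6%. Then 281 × 0.216 = 61, about 36 in West and 25 in Southwest if returners are spread evenly across districts and the share is the same among Lung-RADS 1 or 2 scans. Neither 5.7% nor 21.6% is a bound, because patients first screened before 2020, or who returned after skipping a year, are not counted.

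**4. Later positive scans that the literal criterion leaves open.** Assume 10% of the 287 repeat scans are above Lung-RADS 2: 28.7 city-wide over a year. On the trial's scale, two districts and half a year, 28.7 × 0.47 × 0.5 = 6.7, or about 7 against a planned 281.

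**5. Possible shift in the district comparison (illustration; both inputs assumed).** Shift = difference in repeat share × difference in adherence between repeat and first screeners. A 10-point difference in share with a 20- to 50-point difference in adherence gives 0.10 × 0.20 = 2 points to 0.10 × 0.50 = 5 points. For scale, with 24% in Southwest the design has 80% power for about 40% in West, a difference of about 16 points.

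**The case against.** Several counter-arguments have force.

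- **Including repeat screeners fits the aim.** The hypothesis concerns yearly follow-up in general, and the planning count matches the broad criterion. This stands. It is a reason to correct the Abstract's wording rather than to narrow eligibility.
- **The database is described as holding baseline screens.** That does not settle the matter. If the 1,328 includes the 75 or so people rescanned in 2021, it is not a baseline count. If it leaves them out, the criterion admits patients whom the count omits.
- **Patients whose latest scan is positive.** A reader might infer that the plan deliberately brings them into the 12-month comparison. The documents do not support that. Missed appointments are tied to a Lung-RADS 1 or 2 result, the secondary set to a negative study, and the 90% factor removes positive 2022 scans from the 281. What remains is a gap in the literal criterion.
- **Screening round as a predictor.** A reader might infer that the plan's data show round to predict adherence. They do not. Preliminary Data reports that adherence "varies by baseline Lung-RADS score (21%-70% in Black patients; 32%-88% in White patients"), which concerns the Lung-RADS score. The link with round is plausible but assumed.
- **Power.** A reader might infer that the trial is underpowered. It would lose power only if restricted to first scans (about 220 patients and 71% power at a 21.6% repeat share; about 266 and 79% at 5.7%). Neither the plan's criteria nor the fix below makes that restriction.
- **The criteria are the same in both districts.** That is correct, so they do not by themselves favour either group. Identical criteria do not, however, guarantee an identical mix.

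**Conclusion.** The concern holds in a limited form. The population in the Abstract and the operative criteria disagree, no index scan is defined, and repeat screeners are included. Their share is not given. The documents' own rates suggest about 6% for 2021, and about 22% (61 of 281) if 24% adherence carried over to 2021 scans. Later-positive patients are an unclosed gap of about 7 against 281, assuming that 10% of repeat scans are positive. The sample-size arithmetic and the stated power are not at fault.

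The case for acting rests on the non-randomised design and the absence of screening history from both primary analyses. It is strongest for the logistic model, where patients choose whether to use the programme. That history matters there is a reasonable assumption, not something the documents show. This is an inexpensive improvement that should be made, not a defect that undermines the comparison.

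**What to change.** - **Index scan.** In both districts, define it as the patient's most recent LDCT in the 2020-2022 window, and require that scan to be Lung-RADS 1 or 2. Classify the appointment as upcoming or missed relative to it.
- **Wording.** In the Abstract, replace the reference to a negative baseline scan with the most recent negative screening CT. Use the same definition in Specific Aim 2 and in Recruitment and Sample.
- **Both rounds stay in**, so N remains about 281.
- **Analysis.** Derive first versus repeat screen from existing scan records and add it as a covariate to the logistic model under Evaluation. That model concerns programme use and leaves the chi-squared test unchanged, so also report West versus Southwest adherence separately by round alongside that test.

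**Cost.** One reworded criterion, one derived variable and one more model term. A handful of patients with a later positive scan leave the set, and the stated population becomes slightly broader than baseline.

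### Does the forecast of 281 patients fail because the plan does not say whether an upcoming scan is one that is due or one that is booked?

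*Combined protocol and SAP*

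**What the plan says.** Recruitment and Sample builds the primary sample from the 1,328 Philadelphia residents scanned in 2021, 90% of them Lung-RADS 1 or 2. It proceeds "Assuming the same number of patients receive LCS in 2022 and follow-up LDCT scans are evenly distributed throughout the year", which gives 598 upcoming studies in six months, with 167 in West (28%) and 114 in Southwest (19%). Eligibility in the same section refers to the scan and does not mention a booking: "2) upcoming or missed follow-up LDCT 3) residence in the city of Philadelphia".

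Specific Aim 2 uses appointments. It has "primary analysis focused on patients with upcoming appointments", uses the EHR and RIS "to identify dates of LDCT upcoming appointments over 6 consecutive months", and times the navigator's call two weeks before the appointment. Evaluation states the first primary outcome for patients with upcoming appointments.

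For the secondary analysis, West patients with missed appointments are counted as "66%) following a Lung-RADS 1 or 2 recommendation on LDCT(90%) in 2020 and 2021 will be included, resulting in an additional 278 patients". Preliminary Data reports, for 2020 scans with a Lung-RADS 1 or 2 result, that "adherence to a 12-month follow-up study in 2021 was 24" per cent. It adds: "Data collection from 2022 is still in progress so estimates from 2020 and 2021 were utilized". Power Considerations takes the 281 and claims 80% power for W = 0.17.

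**The concern.** One word seems to cover two populations. The forecast counts everyone whose yearly scan falls due, while the conduct sections describe people who hold an appointment. The two coincide only if every patient due is booked, which the plan does not state.

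The plan's rates do not obviously settle it. If *missed* means the scan was not obtained, 24% adherence implies 76% missed, not 66%. If everyone is booked and 66% miss, then 34% attend, not 24%. If both rates describe the same people, 10% are in neither group, which hints at about 90% booked.

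Two things would be at stake. The 281 supports the only power statement for the primary comparison. The definition also decides whether a patient who is due but unbooked belongs in the intention-to-treat denominator; a call timed from an appointment cannot reach that patient, so including such patients would dilute the effect.

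**Working it through.** **1. The forecast (Recruitment and Sample).** 1,328 × 0.90 / 2 = 597.6, stated as 598. Then 598 × 0.28 = 167.4 and 598 × 0.19 = 113.6, so 167 + 114 = 281. It reproduces.

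**2. The power statement (Power Considerations).** For a chi-squared test with 1 df and two-sided alpha 0.05, the noncentrality is n × W². With n = 281 and W = 0.17 it is 281 × 0.0289 = 8.12, giving power 81.3%. Power of 80% needs noncentrality 7.849, so the smallest W is √(7.849 / 281) = 0.167, which rounds to 0.17. It reproduces.

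**3. The missed-appointment count.** Volumes are those "of the 349 and 1,328 Philadelphia residents who received LCS in 2020 and 2021 respectively": (349 + 1,328) × 0.90 × 0.28 = 422.6, and × 0.66 = 278.9, stated as 278. Replacing 66% by 76% gives 321.2.

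**4. Can 66% and 24% stand together?** The 24% belongs to the 2020 cohort alone, while the 66% is applied to 2020 and 2021.
- Negative scans: 349 × 0.90 = 314.1 in 2020 and 1,328 × 0.90 = 1,195.2 in 2021, total 1,509.3. The 2021 cohort is 79% of the pool.
- Missed share in 2021 needed for a pooled 66%: (0.66 × 1,509.3 − 0.76 × 314.1) / 1,195.2 = 0.634, which is adherence of 36.6%.
- Preliminary Data gives overall adherence of 36% at Penn Medicine. With that for 2021: (0.76 × 314.1 + 0.64 × 1,195.2) / 1,509.3 = 66.5% missed, against the stated 66%.

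This does not prove where the 66% came from: the 36% covers a different population and is not specific to 2021 scans. It does show that the two rates need not conflict, and that applying 76% to the whole pool stretches a 2020 rate over mostly 2021 patients.

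**5. What a booking rate would do.** The documents give none. With an assumed booked share and no offset:

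| Assumed booked share | n | Power at W = 0.17 | Smallest W at 80% power |
|---|---|---|---|
| 100% | 281 | 81% | 0.167 |
| 90% | 253 | 77% | 0.176 |
| 70% | 197 | 66% | 0.200 |
| 50% | 141 | 52% | 0.236 |

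At 90% booked and a control rate of 24%, the detectable West rate moves from 40.1% to 41.0%. If only booked patients count and every attender was booked, the control rate itself rises to 0.24 / 0.90 = 27%. The loss at 90% is cancelled by 2022 volume of 1,328 / 0.90 = 1,476, an 11% rise.

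**6. The operational wording.** Specific Aim 2 selects West patients with an upcoming or missed appointment, takes dates from the EHR and RIS, and times contacts at two weeks, one week and one day before the appointment. Patients who missed are offered a rescheduled one. The education paragraph of Specific Aim 1 and the primary outcome in Evaluation also refer to appointments. A patient without a booking has no date and cannot appear on such a list.

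**The case for a change.** The strongest case for a change has three parts.

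- **Comparability.** Listing by appointment is spelled out only for West. Booked patients in one district set against due patients in the other would bias a non-randomised comparison. That is true, but nothing in the plan suggests different rules: the primary outcome is worded for patients with upcoming appointments in both groups, and the natural reading is one RIS query run twice.
- **Power.** The booked share is unknown and might be well below 90%; at 70% the power would be about 66%. This stands as a sensitivity range. It is not evidence that the stated figure is wrong. The 90% itself comes from adding two rates for different cohorts, which the plan never does.
- **Stratum.** With no listing date, a patient who misses and rebooks within the six months could sit in either stratum. This is a detail of data handling, and an analyst would fix it when the list is drawn.

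It also stands that the 66% has no stated source. It bears only on the secondary West count, not on the 281, the chi-squared test or the power statement.

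**Conclusion.** No change follows. The forecast counts patients falling due and the conduct sections count patients with appointments, so 281 is an approximation whose match to the booked population is not shown. But it is presented as an anticipated number under two stated assumptions, and its arithmetic and power statement reproduce (281; 81% power at W = 0.17). The conduct text points consistently to booked appointments, which largely answers the intention-to-treat question. The test will use whatever patients the two districts supply in six months, so a different forecast would alter neither the conduct nor the analysis.

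The size of any shortfall cannot be derived. It runs from nothing to about 4 percentage points of power at an assumed 90% booked share, and more at lower shares. Growth in 2022 volume could offset it; volume went from 349 to 1,328 in the year before, so the net direction is unknown. The conclusion assumes that one appointment-based rule is applied to both districts, under which the comparison stays valid. What remains is a gap in wording that analysts fill sensibly.
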